13.2. Informed Consent

The principles of informed consent are described in ICH Guidelines for GCP.

The ICF used by the investigator must be reviewed and approved by the sponsor prior to submission to the appropriate IRB/EC. A copy of the IRB/EC-approved ICF and documentation of approval must be provided to the sponsor before study drug will be shipped to the study site.

It is the responsibility of the investigator or designee (if acceptable by local regulations) to obtain written informed consent from each patient prior to his/her participation in the study and after the aims, methods, objectives, and potential hazards of the study have been explained to the patient in language that he/she can understand. The ICF should be signed and dated by the patient and by the investigator or authorized designee who reviewed the ICF with the patient.

- Patients who can write but cannot read will have the ICF read to them before signing and dating the ICF.
- Patients who can understand but who can neither write nor read will have the ICF read to them in presence of an impartial witness, who will sign and date the ICF to confirm that informed consent was given.

The original ICF must be retained by the investigator as part of the patient's study record, and a copy of the signed ICF must be given to the patient.

If new safety information results in significant changes in the risk/benefit assessment, the ICF must be reviewed and updated appropriately. All study patients must be informed of the new

information and provide their written consent if they wish to continue in the study. The original signed revised ICF must be maintained in the patient's study record and a copy must be given to the patient.

The principles of informed consent are described in ICH Guidelines for Good Clinical Practice.

The ICF used by the investigator must be reviewed and approved by the sponsor prior to submission to the appropriate EC. A copy of the IRB/EC-approved ICF and documentation of approval must be provided to the sponsor before study drug will be shipped to the study site.

13.3. Patient Confidentiality and Data Protection

The investigator must take all appropriate measures to ensure that the anonymity of each study patient will be maintained. Patients should be identified by their initials and a patient identification number, only, on CRFs or other documents submitted to the sponsor. Documents that will not be submitted to the sponsor (eg, signed ICF) must be kept in strict confidence.

The patient's and investigator's personal data, which may be included in the sponsor database, will be treated in compliance with all applicable laws and regulations. The sponsor shall take all appropriate measures to safeguard and prevent access to this data by any unauthorized third party.

13.4. Institutional Review Board/Ethics Committee

An appropriately constituted IRB/EC, as described in ICH Guidelines for GCP, must review and approve:

- The protocol, ICF, and any other materials to be provided to the patients (eg, advertising) before any patient may be enrolled in the study
- Any amendment or modification to the study protocol or ICF before implementation, unless the change is necessary to eliminate an immediate hazard to the patients, in which case the IRB/EC should be informed as soon as possible
- Ongoing studies on an annual basis or at intervals appropriate to the degree of risk

In addition, the IRB/EC should be informed of any event likely to affect the safety of patients or the continued conduct of the clinical study.

A copy of the IRB/EC approval letter with a current list of the IRB/EC members and their functions must be received by the sponsor prior to shipment of drug supplies to the investigator. The approval letter should include the study number and title, the documents reviewed, and the date of the review.

Records of the IRB/EC review and approval of all study documents (including approval of ongoing studies) must be kept on file by the investigator.

14. PROTOCOL AMENDMENTS

The sponsor may not implement a change in the design or operation of the protocol or ICF without an IRB/EC-approved amendment.

15. PREMATURE TERMINATION OF THE STUDY OR CLOSE-OUT OF A SITE

15.1. Premature Termination of the Study

The sponsor has the right to terminate the study prematurely. Reasons may include efficacy, safety, or futility, among others. Should the sponsor decide to terminate the study, the investigator(s) will be notified in writing.

15.2. Close-out of a Site

The sponsor and the investigator have the right to close-out a site prematurely.

Investigator's Decision

The investigator must notify the sponsor of a desire to close-out a site in writing, providing at least 30 days' notice. The final decision should be made through mutual agreement with the sponsor. Both parties will arrange the close-out procedures after review and consultation.

Sponsor's Decision

The sponsor will notify the investigator(s) of a decision to close-out a study site in writing. Reasons may include the following, among others:

- The investigator has received all items and information necessary to perform the study, but has not enrolled any patient within a reasonable period of time
- The investigator has violated any fundamental obligation in the study agreement, including but not limited to, breach of this protocol (and any applicable amendments), breach of the applicable laws and regulations, or breach of any applicable ICH guidelines
- The total number of patients required for the study are enrolled earlier than expected

In all cases, the appropriate IRB/EC and Health Authorities must be informed according to applicable regulatory requirements, and adequate consideration must be given to the protection of the patients' interests.

16. STUDY DOCUMENTATION

16.1. Certification of Accuracy of Data

A declaration assuring the accuracy and content of the data recorded on the CRFs must be signed by the investigator. This certification form accompanies each set of CRFs. The signed form will be provided to the sponsor with the final set of CRFs for each patient.

16.2. Retention of Records

The investigator must retain all essential study documents, including ICFs, source documents, investigator copies of CRFs, and drug accountability records for at least 15 years following the completion or discontinuation of the study, or longer if a longer period is required by relevant

regulatory authorities. The investigator must consult with the sponsor before discarding or destroying any essential study documents following study completion or discontinuation. Records must be destroyed in a manner that ensures confidentiality.

If the investigator's personal situation is such that archiving can no longer be ensured, the investigator must inform the sponsor and the relevant records will be transferred to a mutually agreed-upon destination.

17. CONFIDENTIALITY

Confidentiality of information is provided as a separate agreement.

18. FINANCING AND INSURANCE

Financing and insurance information is provided as a separate agreement.

19. PUBLICATION POLICY

The publication policy is provided as a separate agreement.

- resolve or improve after discontinuation of study drug or injection procedure
- reappear or worsen when dosing with study drug or injection procedure is resumed
- are known to be a response to the study drug or injection procedure based upon pre-clinical data or prior clinical data

NOTE: This list is not exhaustive.

Appendix 2: The National Cancer Institute Common Terminology Criteria for Adverse Events

For infusion reactions:

General disorders and administration site conditions					
Adverse Event	Grade				
	1	2	3	4	5
Infusion related reaction	Mild transient reaction; infusion interruption not indicated; intervention not indicated	Therapy or infusion interruption indicated but responds promptly to symptomatic treatment (e.g., antihistamines, NSAIDs, narcotics, IV fluids); prophylactic medications indicated for <=24 hrs	Prolonged (e.g., not rapidly responsive to symptomatic medication and/or brief interruption of infusion); recurrence of symptoms following initial improvement; hospitalization indicated for clinical sequelae	Life-threatening consequences; urgent intervention indicated	Death
Definition: A disorder characterized by adverse reaction to the infusion of pharmacological or biological substances.

PPS	Per protocol set
PT	Preferred term
Q1	First Quartile
Q3	Third Quartile
Q4W	Every 4 (weeks)
Q8W	Every 8 (weeks)
RBC	Red blood cell
Regeneron	Regeneron Pharmaceuticals, Inc.
RMDQ	Roland Morris Disability Questionnaire
SAE	Serious adverse event
SAF	Safety analysis set
SAP	Statistical analysis plan
SAS	Statistical Analysis System
SC	Subcutaneous
SD	Standard Deviation
SE	Standard Error
SF-36	Short Form (36) Health Survey
SOC	System organ class
TEAE	Treatment-emergent adverse event
TJR	Total joint replacement
t_{last}	Time of the last measurable (positive) drug concentration
TrkA	Tyrosine kinase type 1
ULN	Upper limit of normal
WBC	White blood cell
WHO	World Health Organization
WHODD	World Health Organization Drug Dictionary

1. OVERVIEW

This Statistical Analysis Plan (SAP) is intended to be a detailed description (expanding on the statistical analyses described in the protocol) of the definitions and statistical techniques to be used for the analyses of data collected in the R475-PN-1524 study. This SAP will be finalized prior to database lock to ensure the credibility of the study results by pre-specifying the statistical methods for the data analyses before unblinding of treatment assignments.

This plan may be revised during the study to accommodate protocol amendments and adapt to unexpected issues in study execution that may affect planned analyses.

Background/Rationale

This randomized, double-blind, multi-dose, placebo-controlled study is designed to evaluate the safety and efficacy of fasinumab in patients with moderate to severe chronic non-radicular LBP who have a history of intolerance or inadequate pain relief from paracetamol/acetaminophen and at least one oral NSAID and at least one opioid. This subset of patients with chronic LBP represents a patient population with an unmet medical need in whom it would be appropriate to prospectively study the hypothesis that fasinumab provides benefit and has an acceptable safety profile.

Dose selection for this multiple-dose study in patients with chronic non-radicular LBP is based on data from 2 completed fasinumab phase 1 studies in healthy subjects (studies R475-PN-0817 and TDU-11480), as well as data from the completed fasinumab phase 2 proof-of-concept study in patients with pain due to OA of the knee (study R475-PN-0901), and the single-dose proof-of-concept study in patients with sciatic pain (study R475-PN-0908), the dose-range evaluated in an ongoing fasinumab phase 2 study in patients with OA of the knee or hip (study R475-PN-1227), and pharmacokinetic (PK) simulations.

Single SC doses of fasinumab up to 30 mg were well tolerated in healthy male and female subjects (study TDU-11480). Single IV doses of up to 1 mg/kg were also studied in healthy male and female subjects (study R475-PN-0817). In this study, fasinumab was generally well tolerated at all but the highest IV dose (1 mg/kg). Neurosensory AEs, which were transient and not severe, led to expansion of the 1 mg/kg IV cohort and a decision to not dose-escalate beyond this level. In the phase 2 proof-of-concept study of fasinumab in patients with pain due to OA of the knee, multiple IV doses of up to 0.3 mg/kg demonstrated efficacy with regard to pain relief and were well tolerated in Caucasian subjects with pain due to OA of the knee. The phase 2 study in patients with pain due to OA of the knee or hip (R475-PN-1227) evaluated the efficacy and safety of 1, 3, 6, and 9 mg of fasinumab SC every 4 weeks (Q4W).

Results from completed studies evaluating tanezumab in patients with chronic LBP and in patients with pain due to OA indicate that the lowest dose studied may not be adequate to demonstrate efficacy in subjects with non-radicular chronic low back pain. This fasinumab study will therefore evaluate the 2 highest SC doses that were evaluated in the recently completed study (R475-PN-1227) in OA patients (6 mg and 9 mg SC Q4W) and also includes a 9 mg IV fasinumab dose to allow PK, efficacy, and safety comparisons. For patients randomized to SC administration, a loading dose equivalent to 2 times the maintenance dose will be administered on day 1 to achieve steady state concentrations sooner. This approach is supported by PK

simulations based on completed fasinumab studies.

The U.S. Food and Drug Administration (FDA) placed the study on partial clinical hold before enrollment was completed and dosing was prematurely terminated before all randomized patients had completed treatment. The study was enrolling patients with chronic low back pain, some of whom had advanced osteoarthritis, to doses that exceeded those being pursued in the concurrent or planned osteoarthritis studies which limits dosing to 6 mg SC Q8W. Since an event of adjudicated arthropathy was observed in the CLBP study in a patient with advanced OA using a dose higher than that being evaluated in the ongoing OA study, the FDA requested that the study be placed on hold until the protocol could be amended to either remove patients with OA or reduce the doses. A decision was made not to amend the protocol to enable dosing to be resumed. At the time of the clinical hold, 563 patients had been randomized into the study. Patients will be encouraged to remain in the study and be followed for all study visits until completion of the week 36 visit to continue to monitor safety and to allow complete data collection.

The planned analyses take this change into account.

1.1. Study Objectives

1.1.1. Primary Objective

The primary objective of the study is to evaluate the efficacy of fasinumab compared to placebo in reducing LBP, as measured by the change from baseline to week 16 in the average daily LBPI NRS Score.

1.1.2. Secondary Objectives

Secondary objectives of the study are to evaluate the efficacy of fasinumab compared to placebo in treating LBP as measured by:

- Change from baseline to week 16 in the RMDQ total score
- Change from baseline to week 16 in the PGA of LBP score
- Change from baseline to week 2, 4, 8, and 12 in the average daily LBPI NRS score

1.1.3. Safety Objectives

Safety objectives of the study are:

- To assess the safety and tolerability of fasinumab compared with placebo in patients with LBP by evaluating:
 - The percent of patients reporting treatment-emergent adverse events (TEAEs)
 - The percent of patients experiencing clinically significant changes in vital signs, physical exams, laboratory safety tests, and electrocardiograms (ECGs)

- To assess the incidence of anti-fasinumab antibody formation

1.1.4. Other Objectives

Exploratory objectives of the study are:

- To evaluate the efficacy of fasinumab compared to placebo, as measured by the percentage of patients who are responders defined by 30% reduction and 50% reduction from baseline to week 16 for:
 - Average daily LBPI NRS score
 - RMDQ total score
 - PGA of LBP score
- To evaluate the efficacy of fasinumab compared to placebo, as measured by the change from baseline to week 16 in the Medical Outcomes Study (MOS) sleep subscale score
- To evaluate the efficacy of fasinumab compared to placebo, as measured by the change from baseline to week 16 in the Short Form (36) Health Survey (SF-36) subscale scores
- To evaluate the efficacy of fasinumab compared to placebo, as measured by the change from baseline to week 16 in the EuroQol 5 Dimensions 5 Levels Questionnaire (EQ-5D-5L)
- To evaluate the efficacy of fasinumab compared to placebo, as measured by the percentage of patients who use rescue medication for LBP at week 16
- To characterize the PK profile of fasinumab

1.1.5. Modifications from the Statistical Section in the Final Protocol

This SAP is based on Protocol R475-PN-1524 Amendment 3.

1.1.6. Revision History for SAP Amendments

None.

2. INVESTIGATION PLAN

[figure not shown]
2.1. Study Design and Randomization

The study consists of a screening period of up to 30 days (day -37 to day -8), a 7-day pre-randomization period (day -7 to day -1), a 16-week randomized, double-blind, placebo-controlled treatment period (to day 113), and a 20-week follow-up period (Figure 1). Approximately 800 patients will be randomized in a 1:1:1:1 ratio to one of the following 4 treatment groups:

- Fasinumab 6 mg SC Q4W and placebo 9 mg IV Q8W
- Fasinumab 9 mg SC Q4W and placebo 9 mg IV Q8W
- Fasinumab 9 mg IV Q8W and placebo SC Q4W
- Placebo SC Q4W and placebo 9 mg IV Q8W

Randomization will be stratified by baseline LBPI NRS score (<7 , ≥ 7), duration of chronic back pain (<5 years, ≥ 5 years), and maximum Kellgren-Lawrence (K-L) score (≤ 2 , > 2) at any knee or hip joint at screening. For patients randomized to SC administration, a loading dose equivalent to 2 times the maintenance dose will be administered on day 1.

Figure 1 Study Flow Diagram

2.2. Sample Size and Power Considerations

Approximately 800 patients (200 patients per treatment) will be randomized into 4 treatment groups. Assuming a significance level of 0.05 [REDACTED], an enrollment of 200 patients per treatment group will provide at least 91% power to detect a treatment difference [REDACTED] between fasinumab 9 mg SC Q4W and placebo for the mean change from baseline to week 16 in the average daily LBPI NRS score [REDACTED]. The assumed treatment difference and common SD were estimated based on results from a phase 2b multiple dose study of tanezumab (5, 10, and 20 mg IV Q8W) versus placebo and naproxen (500 mg BID) in patients with chronic LBP (Kivitz 2013). The Least Squares (LS) mean change (SE) from baseline to week 16 of -2.18 (0.14) and -1.25 (0.16) for tanezumab 20 mg (n = 295) and placebo (n = 230) were used to estimate the treatment difference and common SD.

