3.1. The Modified Intent to Treat Set (mITT)

The modified intent to treat set (mITT) includes all randomized patients per IVRS who received at least one dose of study drug based on the treatment allocated (as randomized) including data up to 5 weeks after the last dose of study drug.

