3.2. The Full Analysis Set (FAS)

The full analysis set (FAS) includes all randomized patients per IVRS and it is based on the treatment allocated (as randomized). The FAS will be used to perform sensitivity analysis for the primary and selected secondary endpoints.

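### SAP 2.1 and 2.2 still state 800 patients and at least 91% power, although the same SAP records 563 randomized and dosing ended for good

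*SAP*

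**What the plan says.** SAP section 1 (Overview) describes the partial clinical hold. It came before enrollment was complete, and dosing ended before all randomized patients had finished treatment. It gives the number: "At the time of the clinical hold, 563 patients had been randomized into the study". It adds: "A decision was made not to amend the protocol to enable dosing to be resumed". It closes the topic with "The planned analyses take this change into account".

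Section 2.1 then reads "Approximately 800 patients will be randomized in a 1:1:1:1 ratio to one of the following 4 treatment groups". Section 2.2 reads "Approximately 800 patients (200 patients per treatment) will be randomized into 4 treatment groups" and continues that, at a significance level of 0.05, "an enrollment of 200 patients per treatment group will provide at least 91% power to detect a treatment difference" between fasinumab 9 mg SC Q4W and placebo. This matches protocol section 9.2. Neither SAP section calls the figures the original design. Section 1.1.5, headed as modifications from the protocol, lists none. No section gives power, detectable difference or expected interval width for the 563 patients.

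Two other provisions bear on the week-16 information. Section 3.1 defines the primary analysis set (mITT) as "including data up to 5 weeks after the last dose of study drug", and section 5.7.1 repeats that limit. Section 3.2 defines the FAS without it: "The FAS will be used to perform sensitivity analysis for the primary and selected secondary endpoints".

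**The concern.** One document gives two incompatible pictures of the trial's size. Section 1 reports enrollment as closed at 563. Sections 2.1 and 2.2 speak in the future tense of 800. The SAP was revised for the hold elsewhere: it adds the mITT set with its 5-week cut, tests the primary hypotheses without multiplicity control, and reports two interim analyses done after dosing stopped. The sample-size text was left as it stood in the protocol.

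What is at stake is how the 9 mg SC result is read. A reader who takes the 91% from the design section could treat a non-significant result as adequately powered evidence of no effect. At the enrolled size the comparison is less precise than that section says, and the SAP does not say by how much.

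**Working it through.** **Inputs**

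- Planned size 200 per arm, power at least 91%, significance level 0.05 (SAP 2.2). Two-sided testing is stated in protocol 9.1.
- Actual size 563 randomized (SAP 1). Under 1:1:1:1 allocation, 563/4 = 140.75 per arm, which is 70.4% of 200.
- Tests at 0.05 each, since SAP 5.7.1 applies no multiplicity control.
- Source data in SAP 2.2: mean change -2.18 (SE 0.14, n = 295) and -1.25 (SE 0.16, n = 230).
- Redacted: the planning difference, the SD and any dropout allowance. I therefore use two bases.

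**The plan's own figure**

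Difference: 2.18 - 1.25 = 0.93. SDs from SE × √n: 0.14 × √295 = 2.405 and 0.16 × √230 = 2.427, pooled 2.414.

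At 200 per arm the standard error is 2.414 × √(2/200) = 0.241, and the noncentrality is 0.93/0.241 = 3.85. The noncentral t at two-sided 0.05 gives 97.0%. An assumed 25% dropout (150 per arm) gives 91.4%. The stated figure is therefore compatible with the visible data as a lower bound, but it cannot be reproduced exactly.

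**Basis (a): planned power exactly 91% at 200 per arm, two-sided 0.05**

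- Noncentrality at 200: 1.960 + 1.341 = 3.301.
- At 140.75: 3.301 × √(140.75/200) = 2.769.
- Power: Φ(2.769 - 1.960) = Φ(0.809) = 79%.

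If planned power was above 91%, this is higher. If the original calculation used 0.025, the noncentrality at 200 is 2.241 + 1.341 = 3.582. Scaled, it is 3.005, and power at the SAP's 0.05 is Φ(1.045) = 85%.

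**Basis (b): visible source data, no dropout (noncentral t, two-sided 0.05)**

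| | 200 per arm | 140.75 per arm |
|---|---|---|
| Standard error of the difference | 0.241 | 0.288 |
| Power for 0.93 | 97.0% | 89.6% |
| Smallest difference with 91% power | 0.80 | 0.95 |
| 95% CI half-width | 0.47 | 0.57 |

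The half-width ratio is 0.566/0.475 = 1.19. Power of 91% needs 147.8 per arm, rounded up to 148, or 4 × 148 = 592 in total. The enrolled number is 592 - 563 = 29 short.

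**Further loss from the 5-week cut**

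- Week-8 dose: target day 57, window ±7 days, so day 64 at the latest (protocol 5.1 and Table 1).
- mITT data then end at day 64 + 35 = 99.
- Week-16 visit: target day 113, window ±7 days, so day 106 at the earliest. SAP 4.4.1 says the visit-day diary entry is missing for everyone, which leaves six diary days, 100 to 105 at the earliest.

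Within the windows, a patient whose dosing stopped before week 12 therefore gives no week-16 value to the primary analysis. Such a patient still contributes earlier visits through the MMRM, and can contribute a week-16 value to the FAS sensitivity analysis. SAP 6.5 uses nominal visits, so an out-of-window visit could differ.

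The number affected is not in the documents. For an assumed share of the 563, with no recovery through the MMRM, basis (b) gives:

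| Assumed loss | Per arm | Power | Half-width |
|---|---|---|---|
| 10% | 126.7 | 86.3% | 0.60 |
| 20% | 112.6 | 82.1% | 0.63 |
| 30% | 98.5 | 76.7% | 0.68 |

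**The case against.** The strongest reply is that nothing in section 2.2 is false. The sentence is conditional on 200 per group and stays true whatever number was enrolled. Section 1 discloses the hold and the 563 before section 2 begins, so a reader of the whole SAP would not believe that 800 were enrolled. Enrollment and dosing are over, so a restated power changes no decision about size, model or population. Sections 5.5 and 5.7.1 will in any case report the analysis-set sizes and the observed confidence intervals.

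Much of this stands. The 91% is not an arithmetic error, and the correction alters no result. The size of the shortfall is also uncertain. On the visible data with no loss, power is only 1.4 points below 91%. The 79% becomes about 85% if the original significance level was 0.025. The 0.95 against 0.93 comparison needs the visible-source SD and equal arms. The 10–30% loss has no source in the documents, and assuming no MMRM recovery makes those rows pessimistic.

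What the reply does not answer is that the SAP says its planned analyses reflect the hold, yet leaves its only statement of size and power unlabelled and gives no replacement. Observed intervals show the achieved precision only afterwards. They do not correct the stated plan.

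**Conclusion.** The concern holds. The SAP states as current a size and a power that the trial it describes does not have, and supplies no revised figure.

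With equal arms, two-sided 0.05 and no further loss, power at the enrolled size is 89.6% on the visible source data. It is 79% if planned power was exactly 91% at 0.05. Expected precision on the visible SD is 19% worse. The 5-week cut lowers the week-16 information further, by an amount that cannot be computed from the documents. These figures illustrate the shortfall and do not replace the sponsor's own calculation, whose inputs are redacted. This is a labelling and disclosure fault that should be corrected. It does not invalidate the analysis.

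**What to change.** In SAP 2.1 and 2.2:

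- Label 800 patients, 200 per group and at least 91% power as the original design.
- State that 563 were randomized, about 141 per arm under 1:1:1:1.
- Give the pooled, blinded number of patients expected to have a week-16 value inside the 5-week cut.
- For that number, restate the power or the expected 95% confidence half-width for 9 mg SC Q4W versus placebo under the original assumptions.

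Per-arm counts should wait until unblinding. SAP section 7 says the study biostatistician remains blinded at the subject level, and a pooled count respects that.

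The cost is wording in two sections and one blinded count. The only drawback is a less favourable stated figure. No analysis set, model, estimate or test changes.
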